6.1.1 Name of Investigational Agent

CPX-351

6.2 General Concomitant Medications and Supportive Care Guidelines

Patients should be off any prior treatment or line of therapy at least 2 weeks prior to D1 of induction therapy with the exception of hydrea. Hydrea will be allowed at the discretion of the treating physician but must be stopped prior to starting CPX-351.

Necessary supportive measures for optimal medical care will be given throughout the treatment as determined by the treating physician and the patient's medical needs. No concomitant chemotherapy, immunotherapy, or therapy with monoclonal antibodies will be allowed during the study.

Prophylactic antibiotics and antiviral agents (e.g. levofloxacin, valacyclovir, etc.) are recommended while on study; however, the use of these or other drugs will be left to the treating physician's discretion. Use of colony-stimulating factors or combinations

thereof (e.g. G-CSF, GM-CSF, or erythropoietin) are at the discretion of the treating physician and are permitted if judged in the patient's best medical interest. At the D35 (+/- 10 days) bone marrow, if there is no evidence of blasts > 5%, G-CSF will be allowed to improve counts at the discretion of the treating physician.

6.3 Criteria for Removal from Study

In the absence of treatment delays due to adverse events, treatment may continue for one cycle of induction therapy and up to four cycles of consolidation therapy if patients achieve response criteria per section 12.0 or until one of the following criteria applies:

End of Treatment Criteria:

• Disease progression (section 12.0),• Intercurrent illness that prevents further administration of treatment,• The investigator and/or treating physician considers it, for safety reasons, to be in the best interest of the subject. Unacceptable adverse events defined as following:
• Any unacceptable treatment related grade 3 or 4 toxicities that fail to recover to baseline or < Grade 3 in the absence of treatment within 4 weeks• Impaired cardiac function• Severe OR life-threatening hypersensitivity reactions• Grade 4 non-hematological organ toxicities regardless of time to recovery, excluding:
• Grade 4 fatigue, asthenia fever, anorexia or constipation• Grade 4 nausea, vomiting or diarrhea not requiring tube feeding, total parenteral nutrition, or requiring or prolonging hospitalization• Infection, bleeding, or other expected direct complication of cytopenias due to active underlying leukemia• Grade 4 infusion reaction including cytokine release syndrome (CRS), if successfully managed and which resolves within 72 hours• Grade 4 tumor lysis syndrome (TLS) if it is successfully managed clinically and resolves within 7 days without end-organ damage• Grade 4 isolated electrolyte abnormalities that last <72 hours• Patient decision to withdraw from treatment (partial consent) or from the study (full consent),• Pregnancy during the course of the study for a child-bearing participant• Death while patient is on the study

Table 1: End of Treatment Criteria

End of Study Criteria:
CASE 2918
Protocol Version 5.0
18 January 2021

- Patient decision to withdraw from the study (full consent),
- Non-compliance with the study protocol,
- Death while patient is in the follow-up phase,
- Patient completed treatment and follow-up phase per protocol.

Table 2: End of Study Criteria

6.4 Duration of Follow Up

Following completion of active treatment (EOT) and while still on study (Follow up), patients will be followed for survival as for 1 year. During the first 6 months of follow-up, the patient will be seen in clinic as standard of care every 30 days, per the study calendar (section 11.2). The clinical course of all grade 3 or 4 events will be followed until resolution, stabilization, or until it has been determined study treatment or study participation is not the cause. New onset adverse events will not be recorded during follow-up.

Serious adverse events that are ongoing at the end of active treatment (EOT), will necessitate follow-up to determine the final outcome. Any serious adverse events that occur after the study period (EOT) and are considered related or possibly related to study treatment or study participation will be recorded and reported immediately, per institutional review board (IRB) requirement.

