8.4 Reporting Procedures for Serious Adverse Events

For the purposes of safety reporting, all adverse events will be reported that occur through 30 days after the final dose of study drug. Adverse events, both serious and non-

serious, and deaths that occur during this period will be recorded in the source documents. All SAEs should be monitored until they are resolved or are clearly determined to be due to a subject's stable or chronic condition or intercurrent illness(es). Related AEs will be followed until resolution to baseline or grade 1 or stabilization.

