11.2 Calendar

Period	Screening Period	Induction Phase							Consolidation Phase				End of Treatment (EOT)	Follow-up ^g
		1 cycle							Up to 4 cycles					
Day	28 Days	1	2	3	4	5	6-27	35 ^l	1 ^{dij}	2	3	4 - 28		
CPX-351 Administration ^a		X		X		X			X		X			
Informed Consent Form (ICF)		X												
Disease history and prior therapies		X												
History and physical exam ^b		X							X				X	
Vital signs ^b		X	X ^{op}		X ^{op}				X	X ^{op}		X ^{op}		
Concomitant medications		X	X							X			X	
ECOG performance status ^c		X								X			X	
Hematology ^b		X	X	X	X	X	X	X ⁿ	X	X ^e		X ⁿ	X	X ^g
Serum chemistry ^b		X	X	X	X	X	X	X ⁿ	X	X ^e		X ⁿ	X	
Pregnancy test		X	X ^k							X ^k				
Echocardiogram		X ^r	X ^q							X				
Electrocardiogram		X ^r												
Bone marrow biopsy and aspiration ^b		X ^r							X				X	
Disease response assessment ^f		X							X				X	
Correlative analysis blood draw ^m		X							X				X	
Survival follow-up														X ^h
Adverse event assessment									← X →					

- a: During the induction phase all patients will receive 44mg/m². Following the induction phase if patients achieve a response (per section 12.0) they may continue onto the consolidation phase. During the consolidation phase patients will receive 15.4mg/m² (daunorubicin 15.4 mg/m² and cytarabine 35 mg/m²) for up to 4 cycles.
- b: See Appendix IV for required tests.
- c: See Appendix I for performance status grading.
- d: Indicates at +/-3 day window.
- e: Required twice weekly to monitor counts, can be completed at a local laboratory.
- f: See Section 12.0 for MDS response assessment criteria.
- g: Follow up will occur monthly as SOC for the first 6 months of follow-up. See section 6.4 for adverse event reporting requirements.
- h: Survival Follow up will occur bimonthly (60 days) for a duration of 1 year from patient's EOT visit.
- i: During only the first cycle in consolidation phase, CPX-351 must be given no earlier than 35 days after the start of induction and no later than 75 days after the start of induction. There should be 35 days between the start of each subsequent consolidation cycles. Patients must have recovered to ANC >500/ μ L and platelets >50,000/ μ L to be eligible for any consolidation therapy.
- j: Prior to the first cycle of consolidation therapy, patient must have an ECOG PS of 0-2.
- k: Must be negative prior to dosing.
- l: Indicates a +/-10 day window.
- m: 10mL of whole blood will be collected in an extra lab tube for these tests.

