14.0 STATISTICAL CONSIDERATIONS

In determining the sample size for the patient cohort, Minimax Simon's two-stage design (Simon, 1989) will be used. The null hypothesis that the true response rate is 0.1 will be tested against a one sided alternative. In the first stage, 7 patients will be accrued in each arm. If there are two or less responses in these 7 patients, the arm will be stopped. Interim analysis will be conducted to determine the benefit of applying the drug in each arm. In the winning arm, 11 additional patients will be accrued for a total of 18. The null hypothesis will be rejected if 4 or more responses are observed in 18 patients. This design yields a type I error rate of 0.1 and power of 0.8 when the true response rate is 0.3.

Descriptive statistical analysis will be calculated, including histograms or box-plots, proportions, range, means and standard deviations. Fisher's exact test and Wilcoxon rank test will be used in univariate analyses of categorical and continuous variables, respectively. Overall response (CR + CRI +) rate and its 95% CI. Given there is no adjustment for multiple comparisons, need to note the p-values from the univariate analyses will be nominal and not used to infer significance.

Toxicity Monitoring Rules

The following toxicity monitoring plan will terminate the trial early given evidence for excessive rates of toxicity with CPX-351 based on the method of Thall et al.¹⁴ Early termination will be applied to evaluate patients experiencing toxicity defined as any grade ≥ 3 non-hematologic AE that is determined to be at least possibly related to CPX-351. A total of 25 patients will be enrolled. The monitoring rules target a toxicity rate of 20% and assume a non-informative Beta (0.2, 0.8) prior distribution. The trial will stop early for toxicity if $\text{Pr}(\text{Toxicity Rate} > 0.20 | \text{data}) > 0.85$, i.e. stop early if the evidence for excessive toxicity (higher than 20%) for the target population given observed data is sufficiently high (probability > 0.85). Monitoring will be carried out

from the 3rd patient. Table 5 summarizes the resultant stopping boundaries and Table 6 summarizes the trial's operating characteristics.

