APPENDIX II: STUDY DESIGN TIME POINT DEFINITIONS

[figure not shown]
Study Time Points	Definitions
Screening	The screening period will occur over 28 days from the time of consent to day -1.
Induction Period	Day 1 ^a to D35 and/or count recovery
Disease Response	The D35 (+/-10 days) bone marrow.
Consolidation Period	The consolidation period is defined as C2D1 through C5D28. Patients who meet disease response criteria will be eligible to receive up to 4 cycles of consolidation therapy.
End of Treatment (EOT)	The day patients meets the defined EOT criteria (Table 1) and discontinues study treatment.
Follow up	Patient will be followed monthly as SOC every 30 days for the duration of 6 months after EOT.
End of Study (EOS)	The time the patient completes 1 year of follow up and/or patient's death, whichever were to occur first.
a: Day 1 is defined as the first dose of CPX-351	

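### Section 6.4 stops recording new adverse events at end of treatment, Section 8.4 continues to 30 days after the last dose, and Section 14 does not say which window its toxicity count uses

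*Combined protocol and SAP*

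**What the plan says.** Section 6.4 (Duration of Follow Up) places follow-up after EOT: "Following completion of active treatment (EOT) and while still on study (Follow up), patients will be followed for survival". For that period it says "New onset adverse events will not be recorded during follow-up". It keeps one exception, for serious adverse events after EOT that are "considered related or possibly related to study treatment or study participation will be recorded and reported immediately".

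Section 8.4 sets a different limit: "all adverse events will be reported that occur through 30 days after the final dose of study drug". Its next sentence covers serious and non-serious events alike.

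Appendix II defines EOT as "The day patients meets the defined EOT criteria (Table 1) and discontinues study treatment". EOT is therefore not tied to the date of the last dose plus 30 days.

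The cross-references also diverge. Footnote g of the Section 11.2 calendar, on follow-up, says "See section 6.4 for adverse event reporting requirements". Section 13.0 instead sends the reader to Section 8.0 for adverse event reporting.

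Section 14.0 defines the toxicity event as any grade 3 or higher "non-hematologic AE that is determined to be at least possibly related to CPX-351". Seriousness is not required. The rule uses a 20% target rate, and Table 5 counts patients who have had such an event. The toxicity rate is to be reported with a 95% CI. No observation window is given for the rule or the rate.

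**The concern.** A site cannot follow 6.4 and 8.4 together when EOT comes within 30 days of a dose, and Section 14 does not settle which governs. A non-serious, related, grade 3 non-hematologic event that starts after EOT but inside the 30 days is recorded under 8.4 and not under 6.4.

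Two outputs depend on the answer: the toxicity stopping rule, which is the trial's early-termination safeguard, and the final toxicity rate. If sites differ in which section they follow, the count will also mean different things for different patients. Any loss goes one way: the observed rate falls and a boundary is reached later or not at all.

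**Working it through.** **1. The plan's own figures.** Inputs from Section 14: prior Beta(0.2, 0.8), target 0.20, posterior threshold 0.85. The boundary at n patients is the smallest x with Pr(p > 0.20 | Beta(0.2 + x, 0.8 + n − x)) > 0.85. This reproduces all eight Table 5 boundaries: 2/3, 3/6, 4/9, 5/12, 5/15, 6/18, 7/21 and 8/24. The posterior probability is 0.863 to 0.943 at the boundary and 0.617 to 0.835 with one event fewer.

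An exact binomial recursion with looks at 3, 6, …, 24 gives these stopping probabilities:

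| True rate | Table 6 | Look at 24 not counted as early | All eight looks counted |
|---|---|---|---|
| 0.10 | 0.05 | 0.046 | 0.046 |
| 0.20 | 0.27 | 0.270 | 0.276 |
| 0.30 | 0.62 | 0.625 | 0.645 |
| 0.40 | 0.88 | 0.883 | 0.900 |

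The rule therefore performs as stated, provided every qualifying event is seen.

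**2. Days in dispute, from the plan's schedule.** Days in dispute = (last dose day + 30) − EOT day, when positive.

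- Induction, last dose day 5: 5 + 30 = day 35. EOT at a day-35 marrow leaves 0 days. EOT at a day-25 marrow, the earliest allowed, leaves 35 − 25 = 10.
- Consolidation completer, last dose C5D3: 3 + 30 = day 33 of that cycle. EOT at C5D28 leaves 33 − 28 = 5.
- Earlier discontinuation: EOT on day 8 after the day-5 dose leaves 35 − 8 = 27. EOT on a dosing day leaves up to 30.

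**3. Which patients can be missed.** All of the following must hold: no qualifying event up to EOT; EOT within 30 days of the last dose; a related grade 3 or higher non-hematologic event starting in the disputed days; and that event not serious, since 6.4 still captures related serious events.

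**4. Effect on the rule.** Let m be the share of patients with toxicity who are missed in this way. The documents give no value, so m is an assumption, and the range starts at zero. The rule then sees p × (1 − m). With the Table 5 boundaries and all eight looks counted:

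| Assumed m | Observed rate, true 30% | Pr(stop) | Observed rate, true 40% | Pr(stop) |
|---|---|---|---|---|
| 0% | 0.300 | 0.645 | 0.400 | 0.900 |
| 2% | 0.294 | 0.624 | 0.392 | 0.887 |
| 5% | 0.285 | 0.591 | 0.380 | 0.865 |
| 10% | 0.270 | 0.536 | 0.360 | 0.822 |

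The expected toxicity rate falls in the same proportion as the observed rate shown.

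**The case against.** The best counter-argument is that very little is lost in practice.

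- Table 5 counts patients, not events. A patient who stops because of a qualifying toxicity is already counted, and later events change nothing.
- A qualifying event must be at least possibly related, and 6.4 still records related serious events after EOT. Under Section 8.1.2, an event that causes or prolongs hospitalization is serious, with listed exceptions, so many severe events after EOT would be captured.
- On schedule, the gap is 0 to 10 days after induction and about 5 days for a consolidation completer. All adverse events are also documented at the EOT visit.
- Section 13.0 points to Section 8.0, and Section 8.1.3 requires events after consent to be recorded in the medical record. A site that works from Section 8 loses nothing.

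All of this stands as a limit on size, but it does not remove the contradiction. A grade 3 event is serious only if it meets a listed outcome, so non-serious qualifying events can occur, and Section 14 counts them. The reference to Section 8.0 shows that two parts of the protocol send sites to different rules.

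A reader might infer that events are lost selectively in the patients most prone to toxicity, because they stop early. The documents do not support this. Those who stop for a qualifying toxicity are already in the count, and nothing is said about toxicity risk in those who stop for other reasons. A reader might also infer a loss of 10% to 20% of events. No figure in the documents supports a loss of that size.

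**Conclusion.** The inconsistency is in the current text and should be corrected. Following 6.4 as written can undercount the patients who enter the stopping rule and the toxicity rate. The direction is certain: a lower rate and later stopping. The size is unknown and probably small, because only non-serious first qualifying events in the disputed days are affected. At an assumed 2% missed, the stopping probability falls by 0.021 at a true 30% rate (0.645 − 0.624) and by 0.013 at 40% (0.900 − 0.887). At 5% the falls are 0.054 and 0.035. The 10% row is an upper illustration, not an estimate.

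These figures assume that the missed share applies evenly to all patients with toxicity, that looks occur at every third patient, and that the look at 24 counts as a stop. The Table 5 boundaries are not in question.

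**What to change.** Amend Section 6.4 and calendar footnote g to agree with 8.4: all new adverse events, serious or not, are recorded through 30 days after the last dose whether or not EOT has occurred, and related or possibly related serious events are recorded after that. In Section 14, state that the toxicity count for Table 5 and the reported toxicity rate both use this window. Make the references in Section 13.0 and footnote g lead to the same rule.

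The cost is a few sentences and a little more adverse event data entry. Monthly clinic visits in the first 6 months after EOT already exist, so no visit is added. The boundaries in Table 5 and the figures in Table 6 need no change on this account.

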7.0 Dose Delays/Dose Modifications

No dose reductions of CPX-351 will be allowed during the study. Dose delays will be at the discretion of the treating physician after discussion with the PI. Missed doses of CPX-351 can be made up on subsequent days if felt to be in the best interest of the patient. CPX-351 doses must be given at least 24 hours apart. This will be determined by the treating physician following discussion with the PI.

If at any time during an infusion the patient experiences moderate hypersensitivity reactions, discontinuation of that infusion is mandatory. Premedicate with antihistamines and/or corticosteroids prior to all subsequent infusions. If a patient experiences a mild hypersensitivity reaction, regardless of premedication, infusion must be interrupted and can be re-initiated at half the prior rate.

8.0 Adverse Events and Potential Risks

8.1 Definitions

8.1.1 Adverse Event

An **adverse event** (AE) is any unfavorable or unintended event, physical or psychological, associated with a research study, which causes harm or injury to a research participant as a result of the participant's involvement in a research study. The event can include abnormal laboratory findings, symptoms, or disease associated with the research study. The event does not necessarily have to have a causal relationship with the research, any risk associated with the research, the research intervention, or the research assessments.

Adverse events may be the result of the interventions and interactions used in the research; the collection of identifiable private information in the research; an underlying disease, disorder, or condition of the subject; and/or other circumstances unrelated to the research or any underlying disease, disorder, or condition of the subject.

8.1.2 Serious Adverse Events

A **serious adverse event** (SAE) is any adverse experience occurring at any dose that results in any of the following outcomes:

- Results in **death**.
- Is a **life-threatening** adverse experience. The term life-threatening in the definition of serious refers to an adverse event in which the subject was at risk of death at the time of the event. It does not refer to an adverse event which hypothetically might have caused death if it were more severe.
- Requires **inpatient hospitalization or prolongation of existing hospitalization**. Any adverse event leading to hospitalization or prolongation of hospitalization will be considered as Serious, UNLESS at least one of the following expectations is met:
 - The admission results in a hospital stay of less than 24 hours OR

- The admission is pre-planned (e.g., elective or scheduled surgery arranged prior to the start of the study) OR
- The admission is not associated with an adverse event (e.g., social hospitalization for purposes of respite care).

However, it should be noted that invasive treatment during any hospitalization may fulfill the criteria of “medically important” and as such may be reportable as a serious adverse event dependent on clinical judgment. In addition, where local regulatory authorities specifically require a more stringent definition, the local regulation takes precedent.

- Results in **persistent or significant disability/incapacity**. The definition of disability is a substantial disruption of a person’s ability to conduct normal life’s functions.
- Is a **congenital anomaly/birth defect**.
- Is an **important medical event**. Important medical events that may not result in death, be life-threatening, or require hospitalization may be considered a serious adverse experience when, based upon appropriate medical judgment, they may jeopardize the subject and may require medical or surgical intervention to prevent one of the outcomes listed in this definition. Examples of such medical events include allergic bronchospasm requiring intensive treatment in an emergency room or at home, blood disease or disorders, or convulsions that do not result in inpatient hospitalization, or the development of drug dependency or drug abuse. The development of a new cancer is always considered an important medical event.

8.1.3 Adverse Event Evaluation

The investigator or designee is responsible for ensuring that all adverse events (both serious and non-serious) observed by the clinical team or reported by the subject which occur after the subject has signed the informed consent are fully recorded in the

subject's medical records. Source documentation must be available to support all adverse events.

A laboratory test abnormality considered clinically relevant as deemed by the treating physician should be reported as an adverse event.

The investigator or sub-investigator (treating physician if applicable) will provide the following for all adverse events (both serious and non-serious):

- Event term (as per CTCAE)
- Description of the event
- Date of onset and resolution
- **Expectedness of the toxicity**
- **Grade of toxicity**
- **Attribution of relatedness to the investigational agent- (this must be assigned by an investigator, sub-investigator, or treating physician)**
- Action taken as a result of the event, including but not limited to; no changes, dose interrupted, reduced, discontinued, etc. or action taken with regard to the event, i.e. no action, received conmed or other intervention, etc.
- Outcome of event

Descriptions and **grading scales** found in the NCI Common Terminology Criteria for Adverse Events (CTCAE) version **5.0** will be utilized for AE reporting.

An expected adverse event is an event previously known or anticipated to result from participation in the research study or any underlying disease, disorder, or condition of the subject. The event is usually listed in the Investigator Brochure, consent form or research protocol.

An unexpected adverse event is an adverse event not previously known or anticipated to result from the research study or any underlying disease, disorder, or condition of the subject.

Attribution is the relationship between an adverse event or serious adverse event and the study drug. Attribution will be assigned as follows:

- Definite – The AE is clearly related to the study drug.
- Probable – The AE is likely related to the study drug.
- Possible – The AE may be related to the study drug.
- Unlikely – The AE is doubtfully related to the study drug.
- Unrelated – The AE is clearly NOT related to the study drug.

Protocol must specify if attribution is required for individual components of the treatment regimen or the treatment regimen as a whole.

